4.1.2 Subject Training

Study subjects will initially learn about the blinding procedures and the importance of maintaining the blind during the informed consent process. Subjects will be reminded at each follow-up visit that blinding is an essential part of their involvement in the study to maintain the scientific integrity and value of their participation.

Since subjects may visit non-study related physicians during the course of their participation in this study e.g., for emergency or standard care, each subject will be given a study participant card with instructions to present the card to healthcare providers at any non-study related visit. The subject participant card will alert non-study

medical personnel that the subject is in a blinded clinical study and request that they maintain the study blind whenever possible.

The study subject will be questioned at every follow-up to ask if they have become unblinded, and if so, the reason associated with becoming unblinded. The study site personnel will remind the patient that even if they know their group assignment, it is imperative that they do not reveal this to any of the study assessors.

4.1.3 Site Personnel Training

Detailed training specific to each study position will be provided to study site personnel to ensure that the blinding procedure is fully understood (reference Section 4.2: Blinding Procedures).

4.1.4 Randomization

After all pre-randomization assessments have been completed, each subject will be assigned sequentially to one of the two study groups (Treatment or Control), by means of a computer-generated random number scheme created by the Sponsor (reference Section 3.6: Randomization). The study coordinator and limited study personnel (e.g., implanting physician) will also have knowledge of the treatment assignment.

4.2 Blinding Procedures

4.2.1 Index Procedure through Discharge

All subjects will experience similar procedures to ensure that they will not be able to deduce the treatment assignment based on the type of intervention or time associated with the index procedure. If general anesthesia is not used, subjects will wear earbuds while in the catheterization lab to ensure that they cannot hear study personnel discussing randomization or the procedure, and their vision masked (either with a blindfold or with sterile drapes appropriately positioned) so as to ensure they are unable to see any of the catheterization lab monitors.

Catheterization lab personnel will be trained to the importance of maintaining the study blind and to ensure that study subjects are treated similarly during and after the procedure. Recovery room and floor nursing staff will receive training on continued maintenance of the study blind during the recovery period.

4.2.2 Study Follow-Up Visits

Rigorous efforts on the part of the subjects, implanting physicians, heart failure physicians, and supportive personnel will be implemented to ensure that endpoint assessors remain blinded through the 12-month follow-up.

4.2.2.1 Echocardiographic Assessments

The site echosonographer will conduct intra-procedure echocardiographic assessments and cannot be blinded to the subject's treatment assignment. In order to ensure that

study subjects remain blinded during scheduled follow-up echocardiograms, sonographers at each participating site will be instructed on preserving blinding prior to study start. Specific blinding procedures which will be followed by site sonographers, include:

- Keeping the echo screen faced away from the subject during the procedure
- Not discussing any details of the echo results with a study subject
- Not discussing the treatment assignment of a study subject, especially with the blinded study personnel or any non-study hospital staff

All baseline and follow-up echocardiographic analysis will be performed by an independent echocardiography corelab. A designated member of the corelab staff will remove all subject identifying information (including the date and visit interval) and digitally mask the coronary sinus/great cardiac vein (location of device). This will be done for all views required to assess the echocardiographic endpoints related to mitral regurgitation and left ventricular hemodynamics. This will ensure that the designated corelab assessor will always remain blinded.

For those parameters that are unavoidably affected by digital masking (e.g., mitral annular dimensions), an unblinded assessor will be used to gather the most accurate information without hindrance of the digital masking.

Echocardiographic analysis will be done in batches, with multiple subjects (Treatment and Control) at different visit intervals analyzed within the same batch, at the same time, for both consistency and blinding purposes. (Reference Appendix E: Echocardiogram Protocol.)

4.2.2.2 Functional and QOL Assessments

The assessors/administrators of the NYHA classification, six minute walk test and QoL questionnaires (KCCQ and SF12) will not be aware of the subject's group assignment. Other study personnel will be trained to ensure that these assessors are not included in study communications to ensure that they remain blinded.

If a functional assessor/administrator becomes unblinded, a back-up functional assessor is to be used for all future assessments for that subject. Likewise, if a study subject becomes unblinded, steps will be taken to ensure the continued blinding of the assessors.

4.3 Unblinding

The treatment assignment for a subject will be unblinded only in the following circumstances:

- 1) In the event of medical emergency where it is medically necessary to know if the subject received an implant.
- 2) After a randomized study subject has completed their 12-month visit, the treatment assignment for that subject can be unblinded.

The DSMB and/or CEC, upon request, may be provided with the randomization assignment of a particular subject(s) or to assess safety trends between study groups. This can be provided by the study statistician and does not require unblinding of critical site and study personnel.

5 Adverse Events and Risk Analysis

5.1 Adverse Events

The primary measures of safety are based on reported adverse events. Adverse events shall be assessed and documented from the time of consent and through the last study follow-up visit. An underlying disease that was present at the time of enrollment is not reported as an adverse event (AE), but any increase in the severity of the underlying disease during the course of the study shall be reported as an AE. The Investigator shall provide source documentation as requested by the Sponsor, DSMB, and CEC to facilitate adjudication of the adverse event.

5.1.1 Adverse Event Definitions

5.1.1.1 Adverse Event

An adverse event is defined as any untoward medical occurrence, unintended disease or injury, or untoward clinical signs (including abnormal laboratory findings) in subjects, users or other persons, whether or not related to the investigational medical device.

Notes:

1. This definition includes events related to the investigational medical device or the comparator.
2. This definition includes events related to the procedures involved.
3. For users or other persons, this definition is restricted to events related to investigational medical devices.

5.1.1.2 Device Deficiency

Inadequacy of a medical device with respect to its identity, quality, durability, reliability, safety or performance.

Note: Device deficiencies include malfunctions, use errors, and inadequate labeling

5.1.1.3 Malfunction

Failure of an investigational medical device to perform in accordance with its intended purpose when used in accordance with the instructions for use or CIP.

5.1.1.4 Use Error

Act or omission of an act that results in a different medical device response than intended by the manufacturer or expected by the user.

Notes:

1. Use error includes slips, lapses, and mistakes.
2. An unexpected physiological response of the subject does not in itself constitute a use error.

5.1.1.5 Serious Adverse Event

An adverse event is considered serious if it:

- a) results in death,
- b) led to serious deterioration in the health of the subject, that either resulted in
 1. a life-threatening illness or injury, or
 2. a permanent impairment of a body structure or a body function, or
 3. in-patient or prolonged hospitalization, or
 4. medical or surgical intervention to prevent life-threatening illness or injury or permanent impairment to a body structure or a body function,
- c) led to foetal distress, foetal death or a congenital abnormality or birth defect.

Note: Planned hospitalization for a pre-existing condition, or a procedure required by the CIP, without serious deterioration in health, is not considered a serious adverse event.

5.1.1.6 Adverse Device Effect (ADE)

Adverse event related to the use of an investigational medical device.

Notes:

1. This definition includes adverse events resulting from insufficient or inadequate instructions for use, deployment, implantation, installation, or operation, or any malfunction of the investigational medical device.
2. This definition includes any event resulting from use error or from intentional misuse of the investigational medical device.

5.1.1.7 Serious Adverse Device Effect (SADE)

An adverse device effect that has resulted in any of the consequences characteristic of a serious adverse event.

5.1.1.8 Unanticipated Serious Adverse Device Effect (USADE)

Serious adverse device effect which by its nature, incidence, severity or outcome has not been identified in the current study documentation.

Note: Anticipated serious adverse device effect (ASADE) is an effect which by its nature, incidence, severity or outcome has been identified in the risk analysis report.

5.1.1.9 Anticipated Adverse Events

Table 5.1 below provides the list of anticipated adverse events for this study.

Anticipated adverse events are those that are expected to occur in this trial because they are associated with:

- The CARILLON Mitral Contour System device or procedure
- Invasive or stress-inducing tests (cardiac catheterization, transesophageal echocardiography, exercise)
- A heart failure population over time

Reference Section 9.2: Definitions of Terms for the specific definitions of these adverse events.

Table 5.1 Adverse Event Listing

Anticipated Adverse Events	
Angina pectoris (stable or unstable)	Hypotension / Hypertension
Allergic reaction	Infection, generalized
Aneurysm (pseudoaneurysm)	Infection / Inflammatory response at the catheter insertion sites requiring treatment
Anuria	Leukopenia
Aortic Stenosis	Mitral Stenosis
Arrhythmias	Mitral valve injury
Arterio-venous fistula	Myocardial Infarction
Asthenia	Myocardial Ischemia
Bleeding	Nausea / Vomiting
Cardiac tamponade	Pain
Carotid artery trauma	Perforation (arterial, venous or cardiac)
Chronic nerve damage	Pericardial effusion
Coagulopathy	Pericarditis
Deep vein thrombosis	Peripheral ischemia
Dental injury	Pharyngeal and/or laryngeal trauma
Denudation (arterial or venous)	Physical injury
Depression	Pneumonia
Device embolization	Pneumothorax
Device malfunction or failure	Radiation dermatitis
Dissection (arterial or venous)	Renal failure
Dyspnea	Renal insufficiency
Electromechanical dissociation / Pulseless electrical activity	Respiratory distress
Embolism (air, tissue, or thrombus)	Septicemia / Sepsis
Endocarditis	Stroke
Esophageal Injury	Transient ischemic attack
Fatigue	Urinary tract infection
Headache	Vasovagal reaction
Heart failure	Vessel erosion
Heart failure hospitalization	Vessel occlusion (arterial or venous)
Hematoma	Vessel spasm or stenosis (arterial or venous)
Hemolysis	

5.1.2 Recording Adverse Events

All adverse events and device deficiencies occurring during the study, up to and including the study subject's final scheduled visit that are observed by study personnel or reported by the subject will be recorded on the appropriate CRFs, whether or not the event is considered related to the device and/or the index procedure. Reporting will include the event name, onset and resolution date, severity, and assessment of relatedness to placement and use of the CARILLON Mitral Contour System or other suspected cause. Adequate documentation must be supplied with all case reports forms to determine if the adverse event is related to the device or the index procedure.

5.1.3 Description of AE Severity

Mild: awareness of a sign or symptom that does not interfere with the patient's usual activity or is transient, resolved without treatment and with no sequelae.

Moderate: interferes with the patient's usual activity and/or requires symptomatic treatment

Severe: symptom(s) causing severe discomfort and significant impact on the patient's usual activity and requires treatment.

5.1.4 Description of AE Causal Relationship

The causal relationship should be rated as follows:

No = Unrelated: the event is definitely not associated with the investigational device use or procedures

Possible = the temporal sequence between the investigational device use or procedures and the event is such that the relationship is likely or patient's condition or concomitant therapy could have caused the AE

Yes = Definite: the temporal sequence is relevant and the event abates upon investigational device use or procedures completion/removal (dechallenge) or reappearance of the event on repeated device use or procedure (rechallenge).

5.1.5 Reporting SAEs

All serious adverse events and device deficiencies that could have led to a serious adverse device effect (SADE) a) if either suitable action had not been taken, b) if intervention had not been made, or c) if circumstances had been less fortunate must be reported to the study monitor or Cardiac Dimensions within 24 hours of the investigator's first knowledge of the event. The Investigator must forward information about the event promptly and complete the SAE report form provided by the Sponsor, even if the information is incomplete or it is obvious that more data will be needed to form any conclusions.

Additional information regarding the event may be recorded on a follow-up SAE report form and forwarded to the sponsor/monitor. Site personnel will submit follow-up information and the complete event forms to Cardiac Dimensions as the event continues and/or resolves.

It is the responsibility of each Investigator to report all Serious Adverse Events and/or Serious Adverse Device Effects to the Ethics Committee. According to national regulations and Ethics Committee requirements, this reporting requirement can be under the sponsor's responsibility. Upon review of SAE CRFs, Cardiac Dimensions may require the site to provide additional information and source documentation as soon as possible, including, physician notes, lab reports, discharge summaries, other appropriate hospital/ patient records, etc. Source documentation must be supplied as requested by the Sponsor to allow adequate evaluation of the event and its relationship to the study device and procedure.

The sponsor will report all reportable Events to the National Competent Authority in accordance with Medical Devices directives and all applicable official guidelines and national regulations.

5.1.6 Vigilance reporting (EU sites)

At EU sites, vigilance requirements should apply and the site will have to report incidents and complaints to the manufacturer as per their institution's normal procedure.

5.1.7 Data Safety Monitoring Board

In this study, intense and continuous monitoring will occur. A Data Safety Monitoring Board (DSMB), independent of the Sponsor and Investigators, will be convened to assess the progress of the clinical study, including safety data adverse events adjudication and the critical study and subject endpoints at intervals, and to recommend to the Sponsor whether to continue, modify or stop the study.

The DSMB will consist of at least three (3) independent medical professionals who are experts in the fields of cardiology, interventional cardiology, heart failure, or biostatistics, and who are not Investigators.

5.1.8 Clinical Events Committee

A Clinical Events Committee (CEC) will be responsible for adjudicating MAEs, and device (incl. USADEs) and procedural adverse events. The CEC members will be independent medical professionals with expertise in the fields of cardiology, interventional cardiology (including cardiac surgery), or heart failure and without conflict of interest. The CEC will adjudicate to determine if the event is:

- considered a major adverse event
- related to the device (implant and/or catheter)
- related to the procedure
- an anticipated or unanticipated adverse event.

In addition, the CEC will adjudicate events resulting in death to determine whether the death is considered cardiac, non-cardiac, or operative mortality. Members will be provided event data from the clinical study without site or Investigator identification.

5.2 Risk Analysis

Cardiac Dimensions has conducted an analysis of the benefits and risks of the CARILLON Mitral Contour System procedure and the study design for the REDUCE FMR Trial.

5.2.1 Benefits

The major benefit of percutaneous treatment with the CARILLON Mitral Contour System is a potential reduction in mitral regurgitation through a minimally invasive

treatment method, where no current minimally invasive treatment option exists for these subjects. The major potential benefits include:

- Clinical reduction in mitral regurgitation with a non-surgical treatment method
- Improvements in overall function including potential reduction of symptoms associated with dilated cardiomyopathy/mitral regurgitation.

5.2.2 Risks

Risks associated with the CARILLON Mitral Contour System include those risks associated with routine coronary angiography as well as those risks predominantly associated with the delivery and permanent placement of the CARILLON implant. These risks are provided in the CARILLON Mitral Contour System Instructions for Use (reference Appendix A).

5.2.3 Efforts for Risk Minimization

Efforts to minimize risk include the following:

- Clearly defining the subject inclusion/exclusion criteria
- Selecting only qualified, experienced Investigators who have participated in an extensive training program to assure thorough knowledge of the Investigational Plan and proper technique for implantation of the CARILLON implant
- Monitoring angiographic, electrocardiographic and hemodynamic parameters during placement of the implant to evaluate for compromised coronary flow and preclude clinically significant coronary artery compression
- Attending to coronary venous access technique to minimize the trauma to vascular structures
- Ensuring that treatment and follow-up of subjects is consistent with standard and current medical practice
- Providing proctor and/or field clinical technician to offer device related guidance during the implant procedure

If the Investigator and/or the Medical Monitor determine that an adverse event is sufficiently severe to remove the subject from the study, a termination assessment will be performed. The subject will then be given appropriate treatment under medical supervision.

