3.2.2.1 Safety

The following secondary safety endpoints will measure the effect of the CARILLON Mitral Contour System on clinical safety parameters of interest, relative to the Control population

- To document the difference in the rate of major adverse events between randomized groups, at 1 and 12-months post randomization.

Major Adverse Events are defined as a composite of the following:

- Death
- Myocardial Infarction
- Device Embolization
- Vessel Erosion, requiring percutaneous or surgical intervention
- Cardiac Perforation, requiring percutaneous or surgical intervention
- Occurrence of cardiac surgery or percutaneous coronary intervention associated with device failure

- To assess the rate of heart failure hospitalizations (number of admissions, and total associated days in the hospital), from the time of the index procedure through twelve months of follow-up.

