3.2.4 Subject Follow Up Duration

Subjects will be followed for 12 months from the time of randomization to meet primary and secondary endpoints in accordance with the follow-up periods as defined in this *Investigational Plan* and the Subject Study Calendar (reference Appendix C).

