3.8.6 Subject Withdrawal

3.8.6.1 When and How to Withdraw Subjects

A subject may be withdrawn early from the study prior to study completion for several reasons, including but not limited to:

- Loss to follow-up
- Subject consent withdrawal
- Heart transplantation or other confounding intervention
- Physician discretion (for patient health reasons)

If a subject is withdrawn early from the study for any reason, the Cardiac Dimensions clinical study monitor must be notified by telephone, facsimile or e-mail. The Investigator or designee must document the reason for the termination of enrollment and advise Cardiac Dimension of situations that are not resolved.

A subject should not be considered lost to follow-up until three or more attempts have been made to contact the subject and all attempts have failed. One of these attempts should be a letter sent using certified mail with signature confirmation.

If a subject is withdrawn from the study early, the study investigator should contact the patient's heart failure doctor to discuss their involvement in this study and the ongoing medical treatment plan for the subject.

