3.8.6.3 Data Collection and Follow-up for Withdrawn Subjects

If a subject withdraws consent to participate in the study, attempts should be made to obtain permission to record survival data through the 1-year follow-up period.

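### Protocol 5.2.3 and 3.8.6 allow removal from the study for a severe adverse event without providing for collection of later safety outcomes to 12 months

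*Protocol*

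**What the plan says.** Protocol 5.2.3 gives the Investigator and the Medical Monitor, together or singly, a route to remove a subject: if they "determine that an adverse event is sufficiently severe to remove the subject from the study, a termination assessment will be performed". The next sentence reads "The subject will then be given appropriate treatment under medical supervision". No study data collection after that point is mentioned. The termination assessment is not defined, and it appears in neither the protocol's schedules nor the SAP flowchart. Section 3.8.6.1 lists the physician's discretion on health grounds among the reasons for early withdrawal.

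Section 3.8.6.3 is the section on data from withdrawn subjects. It begins "If a subject withdraws consent to participate in the study, attempts should be made to obtain permission to record survival data", up to one year. It does not address subjects who are removed without withdrawing consent.

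Other sections assume complete follow-up. Section 3.2.4 states "Subjects will be followed for 12 months from the time of randomization to meet primary and secondary endpoints". Section 3.2.2.1 sets the safety aim "To document the difference in the rate of major adverse events between randomized groups, at 1 and 12-months post randomization". Section 3.8 requires randomized subjects to complete all visits, and 6.2 adopts intent-to-treat. SAP 2.4.3.1 analyses MAEs and heart failure hospitalizations through 12 months. Section 5.1, however, ties the collection window to study visits: "Adverse events shall be assessed and documented from the time of consent and through the last study follow-up visit".

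**The concern.** Removal under these rules is triggered by an outcome. A subject removed after a severe event may well have a different later risk from one who stays, so the missing follow-up cannot be assumed to be uninformative.

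Leaving the study also does not end exposure for an implanted subject. Section 2.1 describes the implant as permanent, and 2.2 describes recapture only before decoupling. Such a subject would also miss any remaining imaging with device-integrity assessment at 6 and 12 months (3.8.2, 3.8.3).

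The loss could differ between arms. Device embolization and intervention for device failure cannot occur without a device. Under 4.1.4 the implanting physician and the coordinator know the assignment, and nothing requires the removal decision to be made blind. At stake are the 12-month comparisons of MAEs, heart failure hospitalizations, mortality and SAEs.

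**Working it through.** **Step 1: what is collected after removal for an adverse event.**
- 3.8.6.1: the reason is documented and the sponsor is told of unresolved matters.
- 5.1.5: for an SAE, follow-up information is sent while that event continues or until it resolves.
- 5.1.6: EU sites report incidents and complaints under vigilance rules.
- 3.8.6.3: survival only, and only after consent is withdrawn.

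The first two items track the triggering event, and the third is not endpoint collection. None requires new MAEs, heart failure hospitalizations, SAEs or deaths to be sought to 12 months. A subject who withdraws consent may thus have survival recorded, while for a subject removed because of harm nothing is specified.

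**Step 2: what the SAP does with such a subject.** The adverse event layout (SAP 4.3.1) divides by the total number of patients, so a removed subject counts as event-free after removal. SAP 2.1.2 bases categorical percentages on non-missing observations, under which the subject would be dropped. The SAP does not say which applies to MAEs and gives no censoring rule. Last observation carried forward (SAP 2.1.1) would carry forward an event-free status and cannot recover an unobserved event.

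**Step 3: the plan's own figure.** There is none for removals. The only loss figure is the allowance of about 30% attrition in 6.7, set for the primary endpoint: 120 × 0.70 = 84 evaluable subjects, above the 76 required. A two-sample t-test calculation reproduces 76 (57 + 19, power 81.8%). This protects the power for regurgitant volume and has no bearing on unobserved safety events.

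**Step 4: illustration.** From the documents: 120 subjects at 3:1, so 90 Treatment and 30 Control. Assumed: a fraction r of Treatment subjects is removed after a severe event that is not an MAE, and a fraction q of those later has a first MAE. Missed first MAEs = 90 × r × q.

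| r | Removed | q = 20% | q = 40% |
|---|---|---|---|
| 2% | 1.8 | 0.36 | 0.72 |
| 5% | 4.5 | 0.9 | 1.8 |
| 10% | 9.0 | 1.8 | 3.6 |

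For the rate, assume also a 12-month MAE risk of 15% in subjects not removed. True rate = (1 − r) × 15% + r × q.
- r = 5%, q = 40%: 14.25% + 2.0% = 16.25%. Reported: 14.25% if removed subjects count as event-free, 15.0% if dropped.
- r = 10%, q = 40%: 13.5% + 4.0% = 17.5%. Reported: 13.5% or 15.0%.

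One missed MAE moves the Treatment rate by 1/90 = 1.1 points and the Control rate by 1/30 = 3.3 points.

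**The case against.** The best defence is that 5.2.3 never says follow-up ends. Sections 3.7.2 and 3.8 require 12 months of follow-up for Implanted, Non-implanted and Control subjects, with no exception for adverse events, so a sponsor could read them as prevailing. It is true that the end of follow-up is an inference. It is nevertheless the natural reading of removal from the study with a termination assessment, and the contradiction should not be left to sites to resolve.

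Several limits also stand.
- An MAE that itself prompts removal has already been counted in a per-patient rate. Only first MAEs after a different severe event are lost from that rate, together with later deaths, hospitalizations and SAEs.
- Serious procedural problems are partly covered by 3.7.1.2: when a device is recaptured after an attempt, the subject is followed through 12 months.
- Continued exposure applies to Implanted subjects only; the removal rule covers everyone.
- The affected endpoints are secondary or observational, and Protocol 6.8 reports them descriptively.

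These points narrow the loss without closing the gap.

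**Conclusion.** The point holds as a conflict between the removal rules and the 12-month randomized safety comparison. Subjects can leave for outcome-related reasons, and no text requires their later safety outcomes to be collected. It should be corrected, although it does not touch the sample size or the main efficacy test statistic.

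The illustrative size is about 1 to 2 missed MAEs at 5% removal among 90 Treatment subjects, resting on assumed later risks of 20% to 40%. The documents supply neither the removal rate nor those risks.

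Three stronger readings are tempting and not supported:
- *That the loss favours the device.* This is plausible, because some events need a device. But the rule covers both arms, and a missed Control event moves its arm's rate three times as far, in the opposite direction. The net direction is unknown.
- *That the missed events rival the whole expected MAE count.* That would follow from setting 12-month losses against the 30-day rates of 1.9% and 2.8% in 1.3.6. The time frames differ, and 1.3.6.1 also reports 13% at 30 days, which would be 0.13 × 90 = 11.7 events.
- *That the discretion to remove a subject must go.* The defect is in data collection, which can be repaired without changing that discretion.

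**What to change.** Leave the clinical discretion to stop study procedures as it is, and separate it from the end of data collection.

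1. Extend 3.8.6.3 to every early withdrawal or removal other than withdrawal of consent: vital status, MAEs, SAEs and heart failure hospitalizations are collected by visit, telephone or records through 12 months after randomization. Keep the existing survival provision for subjects who withdraw consent.
2. Define the termination assessment and add it to the schedule, or delete the term.
3. State in the SAP that these subjects stay in the intent-to-treat safety analysis, and which denominator applies to the MAE rate.
4. Reconcile 5.2.3, 3.8.6.1 and 3.8.6.3 with 3.2.2.1, 3.2.4 and 3.8.

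The cost is a few sentences of protocol and SAP wording, plus a few extra telephone or record checks.
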